Aim 1: Demonstrate that 5-HT_{1b} activation reduces the reinforcing effects of cocaine. The primary hypotheses, related to our first specific aim, are that: 1) cocaine will function as a reinforcer on the concurrent progressive-ratio choice task that was developed and validated in our laboratory ([name] et al., 2016; 2020) and 2) zolmitriptan will attenuate the reinforcing effects of cocaine, leading to the reallocation of behavior towards the non-drug alternative (i.e., \$6.00) available on the choice task.

Aim 2: Demonstrate that 5-HT_{1b} activation attenuates subjective abuse-related effects of cocaine (e.g., positive subjective effects, craving). The primary hypotheses related to our second specific aim are that: 1) cocaine will produce prototypic effects on subjective outcomes (e.g., increased ratings of drug liking) and 2) zolmitriptan will attenuate these effects (e.g., reduce cocaine related increases on ratings of drug liking).

Aim 3: Demonstrate that 5-HT_{1b} activation attenuates impulsive responding that is a common characteristic of cocaine use disorder and is mediated by the 5-HT system. The primary hypothesis related to our third specific aim is that zolmitriptan will attenuate impulsive responding (e.g., reduce delay discounting of drug and money). This hypothesis is based upon our previous findings and the preclinical outcomes described above.

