Self-Administration Task. After sampling the intravenous cocaine dose (0, 10, and 30 mg/70 kg), subjects will complete 5 choice trials between that dose and \$6.00, separated by 60 minutes. The money amount was selected based on previous research because it functions as a reinforcer but does not completely suppress drug-taking behavior ([name] et al., 2020). The initial response requirement for either choice (i.e., cocaine or money) will be 400 mouse clicks. Response requirements will increase by 200 responses for previously chosen options. For example, if a subject chooses cocaine at the first opportunity, the next response requirement for cocaine would be 600 responses, but the response requirement for money would remain at 400 responses. If a subject were to choose one option exclusively, the response requirements would be 400, 600, 800, 1000 and 1200 responses. These response requirements were based on our previous human laboratory studies that have tested various ratio parameters to maximize drug-maintained responding while minimizing placebo self-administration ([name] et al., 2016; 2020; Sevak et al., 2010; [name] et al., 2010). Subjects may choose not to complete a ratio for either reinforcer during a choice trial (i.e., an omission), but physiological measures and the assessment battery will still be completed as scheduled and the ratio requirements for each reinforcer will carry forward to the next trial. Break points for cocaine and money will be the primary outcome variables.

Assessment Battery. A battery of subjective and cognitive tasks will also be used to assess drug effects to meet Aims 2 and 3. Standard safety and tolerability measures will also be included.

Subjective Outcomes (Appendix A). Two valid and widely used questionnaires that measure various aspects of mood and drug effects will be included: 1) Drug-Effect Questionnaire ([name] et al., 2003) and 2) Adjective Rating Scale (Oliveto et al., 1992). The Cocaine Craving Questionnaire (Dudish-Poulsen and Hatsukami, 1997) will also be included. These measures will be completed prior to each cocaine sampling dose and at 15-minute intervals after administration of the sampling dose.

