Aim 2: Demonstrate that 5-HT_{1b} activation attenuates subjective abuse-related effects of cocaine (e.g., positive subjective effects, craving). Three sets of analyses will be conducted on the subjective effect data. First, data will be analyzed as peak effect (i.e., maximum effect observed following administration of cocaine sampling doses) using two-factor repeated-measures ANOVA. Cocaine (0, 10, and 30 mg/70 kg) and zolmitriptan (0, 2.5, 5, and 10 mg/day) will be factors for these analyses. A significant augmentation or attenuation of the effects of cocaine will be inferred if the main effect of the zolmitriptan or the cocaine-zolmitriptan interaction attains statistical significance in the ANOVA. If the cocaine-zolmitriptan interaction attains statistical significance, the MSE term will be used to conduct Tukey's HSD *post-hoc* test to make appropriate pair-wise comparisons between means. Second, Area Under the Curve (AUC) will be calculated for each subject using the trapezoidal method and analyzed in the same fashion as peak-effect data. Third, these data will be analyzed by repeated-measure ANOVA with cocaine, zolmitriptan and time as factors. The MSE term for the cocaine-zolmitriptan-time interaction will then be used to conduct Tukey's *post-hoc* tests to make appropriate pair-wise comparisons.

Aim 3: Demonstrate that 5-HT_{1b} activation attenuates impulsive responding that is a common characteristic of cocaine use disorder and is mediated by the 5-HT system. For the impulsivity outcomes, each of which have only one data point for each dose condition, data will be analyzed using two-factor repeated-measures ANOVA. Cocaine (0, 10, and 30 mg/70 kg) and zolmitriptan (0, 2.5, 5, and 10 mg/day) will be factors for these analyses. A significant augmentation or attenuation of the effects of cocaine will be inferred if the main effect of the zolmitriptan or the cocaine-zolmitriptan interaction attains statistical significance in the ANOVA. If the cocaine-zolmitriptan interaction attains statistical significance, the MSE term will be used to conduct Tukey's HSD *post-hoc* test to make appropriate pair-wise comparisons between means.

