Physiological data. Three sets of analyses will be conducted on the cardiovascular outcomes and body temperature data. First, data will be analyzed as peak effect using two-factor repeated-measures ANOVA. Cocaine (0, 10, and 30 mg/70 kg) and zolmitriptan (0, 2.5, 5, and 10 mg/day) will be factors for these analyses. A significant augmentation or attenuation of the effects of cocaine will be inferred if the main effect of the zolmitriptan or the cocaine-zolmitriptan interaction attains statistical significance in the ANOVA. If the cocaine-zolmitriptan interaction attains statistical significance, the MSE term will be used to conduct Tukey's HSD *post-hoc* test to make appropriate pair-wise comparisons between means. Second, AUC will be calculated for each subject using the trapezoidal method and analyzed in the same fashion as peak-effect data. Third, these data will be analyzed by repeated-measure ANOVA with cocaine, zolmitriptan and time as factors. The MSE term for the cocaine-zolmitriptan-time interaction will then be used to make appropriate pair-wise comparisons.

Safety and tolerability data. For items from the UKU, which will have one data point per day, data will be analyzed using a two-factor repeated-measures ANOVA. Zolmitriptan (0, 2.5, 5, and 10 mg/day) and day will be factors for these analyses. The MSE term for the zolmitriptan-day interaction will then be used to make appropriate pair-wise comparisons.

Evaluating Relevant Biological Variables. We will conduct exploratory analyses to evaluate potential effects of relevant biological variables. Specifically, we will repeat the analyses described above including factors like sex, age, race, and other drug use to determine whether and how these variables might influence study outcomes. Although exploratory, these outcomes can inform future grant applications in terms of how individual differences influence responses to 5-HT_{1b} activation in people with cocaine use disorder.

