9. POTENTIAL RISKS

The behavioral and physiological assessment procedures employed in this study are benign. The risks to the study subjects are those related to the administration of the drugs under study. Cocaine has safely been administered to human subjects under controlled-laboratory conditions. The relative safety, as well as the contraindications and possible side effects of cocaine and zolmitriptan are well known and documented. However, the administration of any drug involves some risks simply because individuals differ in their reactions

to drugs. The main risk is that subjects will experience side effects that may be unpleasant. The side effects of zolmitriptan and cocaine may change as a function of the drug combinations, which is why we will not be dosing more than the recommended daily amount of zolmitriptan (i.e., 10 mg/day) in this study.

Common side effects of zolmitriptan include dry mouth, nausea, pain/pressure in neck or throat, drowsiness, weakness, warmth, redness or mild tingling under the skin, increased heart rate and increased blood pressure. More serious side effects include chest pain, sudden lateral numbness or weakness, sudden headache, confusion, problems with vision, speech or balance, dizziness, severe stomach pain, hematochezia, serotonin syndrome and cyanosis.

Common side effects of cocaine include anxiety, restlessness, diuresis, irritability, suppressed appetite, insomnia, gastrointestinal upset, increased heart rate, increased blood pressure, palpitations, and arrhythmias. More serious side effects following the chronic, unsupervised administration of much higher doses of cocaine have occurred and include psychotic episodes, suppressed breathing, seizures, myocardial infarctions, heart failure and death.

The doses to be administered in the present experiment were chosen to minimize, if not eliminate, the chance of these side effects occurring since these side effects are related to dose. Thus, it is unlikely that subjects will experience side effects during the experimental protocol. All experiments proposed in this application will be conducted at the CRU and under medical supervision. Side effects of the drugs are temporary, usually dissipating in less than 24 hours.

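### Peak and AUC have no stated baseline reference and a zolmitriptan main effect alone counts as a change in cocaine's effect, so a shift in the resting level can be mislabelled

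*Combined protocol and SAP*

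**What the plan says.** All places are in the combined protocol and SAP.

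- **Subjective peak** (section 7, Data Analysis, Aim 2): "data will be analyzed as peak effect (i.e., maximum effect observed following administration of cocaine sampling doses".
- **Subjective AUC** (same place): "Area Under the Curve (AUC) will be calculated for each subject using the trapezoidal method and analyzed in the same fashion as peak-effect data".
- **Physiological measures** (section 7, Physiological data): "First, data will be analyzed as peak effect using two-factor repeated-measures ANOVA", with peak not defined further. For AUC, "AUC will be calculated for each subject using the trapezoidal method and analyzed in the same fashion as peak-effect data".
- **Inference rule** (both places): augmentation or attenuation of cocaine's effects "will be inferred if the main effect of the zolmitriptan or the cocaine-zolmitriptan interaction attains statistical significance in the ANOVA".
- **Pre-dose readings.** For the questionnaires (section 7, Subjective Outcomes): "These measures will be completed prior to each cocaine sampling dose and at 15-minute intervals after administration of the sampling dose". Heart rate, blood pressure and temperature are also recorded before cocaine (section 7, Cardiovascular Measures and Body Temperature).
- **Timing.** Maintenance medication is taken at 0700 h, baseline measures start at 0800 h and the sampling dose is given at 1000 h (section 7, General Procedures and Table 2).
- **Zolmitriptan's own effects** (section 9): the common side effects listed include "increased heart rate and increased blood pressure".

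No change score, baseline subtraction or baseline covariate appears anywhere in the plan.

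**The concern.** Zolmitriptan is on board when the pre-dose reading is taken. Any effect it has on the resting level is therefore there before cocaine, and equally in the 0 mg cocaine session of each maintenance condition. In the two-factor ANOVA of an unreferenced peak or AUC, such a shift is a zolmitriptan main effect, and the written rule accepts that as evidence that cocaine's effect was augmented or attenuated.

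The measures exposed are those with a non-zero resting level: craving, the adjective ratings, heart rate, blood pressure and temperature. Drug-Effect Questionnaire items mostly ask what the drug is doing, so they have little pre-dose level to shift. At stake is whether a finding on craving, which Aim 2 names, or on the cardiovascular response to the combination describes an interaction with cocaine or only zolmitriptan acting alone.

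**Working it through.** **The plan's own figure.** The plan gives no number on this point. Its one power statement (80% power for f = 0.27, 20 completers) can be reproduced. With four zolmitriptan levels and an assumed correlation of 0.5, λ = f²·n·m/(1−ρ) = 0.0729 × 20 × 4 / 0.5 = 11.66 on 3 and 57 df, giving power 0.7995. That figure does not depend on the baseline question.

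**Structure.** Write a reading as subject level + zolmitriptan resting shift z + cocaine response × time profile + session deviation + reading error. If z is constant within a session and zolmitriptan leaves the cocaine response alone:
- on raw values, z is in every cell, so it enters the main effect and contributes nothing to the interaction;
- on change from pre-dose, z cancels.

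**Assumed inputs (not in the documents).** One pre-dose and four post-dose readings 15 min apart; reading SD 4; session SD s = 4, 6 or 8; shift at the four doses equal to 0, 25, 50 and 100% of the top-dose value; cocaine response 0/8/18 units with post-dose profile 1, 0.8, 0.6, 0.4; sphericity.

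**Closed form for raw AUC** (s = 6, top-dose shift 4). AUC/60 weights the five readings 1/8, 1/4, 1/4, 1/4, 1/8.
- Reading variance: 16 × (2/64 + 3/16) = 3.5.
- Variance per zolmitriptan mean over three cocaine sessions: (36 + 3.5)/3 = 13.17.
- Shifts 0, 1, 2, 4 have mean 1.75 and sum of squares 3.0625 + 0.5625 + 0.0625 + 5.0625 = 8.75.
- λ = 20 × 8.75 / 13.17 = 13.29 on 3 and 57 df, so the main effect is significant in 0.853 of trials. Simulation gave 0.854.

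**Simulation of the plan's rule** (2,000 runs per row; the first three result columns show main effect or interaction significant at 5%, with no true change in cocaine's effect):

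| Session SD | Top-dose shift | Raw peak | Raw AUC | Change peak | Interaction alone, raw peak |
|---|---|---|---|---|---|
| 4 | 2 | 45.8% | 56.4% | 9.7% | 4.6% |
| 4 | 4 | 97.1% | 99.6% | 10.0% | 4.8% |
| 6 | 2 | 29.1% | 32.0% | 10.5% | 5.0% |
| 6 | 4 | 81.0% | 86.2% | 10.0% | 5.0% |
| 8 | 2 | 22.2% | 23.3% | 10.1% | 5.2% |
| 8 | 4 | 57.2% | 61.2% | 10.6% | 5.0% |

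The roughly 10% for change scores is what two 5% tests give: 1 − 0.95² = 9.75%.

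**A second model for heart rate** (subject SD 9, subject-by-zolmitriptan SD 2, cocaine effects 0/10/20 bpm). The raw-peak main effect is significant in about 62%, 43% and 29% of trials at s = 4, 6 and 8 for a 3 bpm shift, and in 97%, 89% and 71% for 5 bpm. Repeat runs differ by a point or two. Change from pre-dose gives 4% to 7%.

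**Limits of referencing alone.**
- If zolmitriptan's effect drifts by 2 bpm after the pre-dose reading at the top dose, the change-score main effect is significant in about 42% of trials. The interaction stays at 4% to 5%.
- For a single reading, session-level error variance is s² + 16 raw and 16 + 16 = 32 for change. They are equal at s = 4, where the within-subject pre/post correlation s²/(s² + 16) is 0.5.
- With a true 40% reduction of a 20 bpm cocaine effect at the top dose, interaction power (raw against change) is 67% v 69%, 42% v 68% and 26% v 66% at s = 4, 6 and 8. At s = 2 (correlation 4/20 = 0.2) it is 94% v 67%.

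**The case against.** The strongest reply is that the design already controls for a resting shift. Every zolmitriptan dose is paired with a 0 mg cocaine session, and the interaction test keeps its 5% level on raw data. That is right, and it shows that the inference rule is as much the cause as the missing baseline. It does not rescue the plan as written, because the plan accepts the main effect alone.

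Several stronger readings are tempting, and the documents do not support them.
- *That the plan uses raw values.* It is silent. Peak effect could be meant as a change, but the only definition given is a post-dose maximum.
- *That the trial would report a false interaction.* No size for a resting shift is given. Section 7 adds 1.5 maintenance days so that transient side effects can subside, and the limits on dosing at high heart rate or blood pressure may truncate an upward shift. The three-factor analysis with time might expose a pre-dose shift, but the plan does not say that pre-dose is a time level, and that analysis does not override the peak and AUC rule.
- *That Aim 2 itself requires an increase over pre-dose.* Its example, "reduce cocaine related increases on ratings of drug liking", concerns drug liking, a Drug-Effect Questionnaire item that is hardly exposed.
- *That omitting the baseline generally hides true interactions.* This depends on the pre/post correlation, which the documents do not give, and it reverses when that correlation is low.
- *That a maximum is wrong for items a stimulant may lower.* This is a separate question; the plan does not list such items, and maximum effect can mean largest departure.

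**Conclusion.** The point holds in a conditional form. For measures with a non-zero resting level, the absence of a stated baseline reference, combined with a rule that a zolmitriptan main effect suffices, allows a pure resting shift to be labelled augmentation or attenuation of cocaine's effect. Under the heart-rate assumptions, the raw-peak main effect is significant in about 30% to 63% of trials for a 3 bpm top-dose shift and about 70% to 98% for 5 bpm, against about 5% for change from pre-dose.

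These percentages rest on assumed SDs, shift sizes and response shape, and on a shift that is constant through the session. The 5-point adjective and craving scales were not simulated. The outcomes concerned are secondary and tertiary (section 17); the primary break points and the Drug-Effect Questionnaire items are little affected. The amendment is worth making before analysis, because it changes what a significant result would be taken to mean.

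**What to change.** Amend Aim 2 and Physiological data in Data Analysis as follows, for the adjective, craving, cardiovascular and temperature measures.

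1. Define peak and AUC relative to that session's pre-dose reading, as a change score. Where the pre/post correlation may be low, use the pre-dose value as a session-level covariate. This needs a mixed model, since the covariate varies by session. A covariate does not fully cancel a shift in the zolmitriptan main effect: with session SD 6 and reading SD 4 the slope is about 36/52 = 0.69, so about 31% of the shift remains. Item 2 is therefore needed as well.
2. Base any statement of augmentation or attenuation on the cocaine-zolmitriptan interaction.
3. Report a zolmitriptan main effect, and the pre-dose reading by zolmitriptan dose, as zolmitriptan's own effect.
4. Keep raw physiological peaks alongside, for comparison with the absolute safety thresholds in sections 7 and 10.
5. State whether the pre-dose reading is a level of the time factor in the third analysis.

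The cost is analysis wording only, since the readings are already collected. The downside is that change scores lose interaction power when the within-subject pre/post correlation is below about 0.5, and gain it only when session-to-session variation is large. The choice between change score and covariate should be fixed in advance for each measure.

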17. DATA AND SAFETY MONITORING

Data Monitoring Plan

Data will be collected using a computerized data collection and management system wherever possible. This system automates the collection of data, which ensures the accuracy and completeness of data collection. The data are stored in a unique file on the hard drive of the computer and are printed after all the tasks are completed. In all instances, the data files do not contain the name of the subject, but instead, a unique four-digit number identifies each subject. A computer file linking the unique number with the subject's name will be kept on a stand-alone, password-protected computer. All data requiring hand entry (e.g., cardiovascular measures) will be double entered by two separate staff members and comparison macros run to ensure accuracy. Data files for experimental tasks and physiological measures from each experimental session will be manipulated and combined into a single electronic spreadsheet for each subject by the PI. Data for all subjects will then be combined into a single electronic spreadsheet and separated by experimental measure for statistical analysis.

The primary outcomes will be the break points for drug and money in the cocaine self-administration task, analyzed as a function of zolmitriptan maintenance conditions. Secondary outcome measures will be abuse-related subjective and cognitive effects of cocaine, analyzed as a function of zolmitriptan maintenance conditions. Tertiary outcome measures will be the physiological and side-effects of cocaine, analyzed as a function of zolmitriptan maintenance conditions. Data will be analyzed using repeated measure ANOVA. The alpha level will be set at 5%.

As noted above, wherever possible, data are collected using an automated computer system, which increases the accuracy and completeness of data collection and ensures the validity and integrity of the data. The initial data manipulation described above will be conducted twice and compared. The quality of manipulated data and data analyses will be monitored by random inspection by the PI and/or Co-Investigators.

Safety Monitoring Plan

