APPENDIX A

Subject-Rated Drug-Effect Questionnaires

Adjectives Rating Scale (ARS)

Individual questions are presented sequentially, one at a time. Subjects rate their response to each question on a 5-point scale (0 = Not at all, 1 = A little, 2 = Moderately, 3 = Quite a bit, 4 = Extremely).

(1) How "ACTIVE" do you feel right now? (2) How "AGITATED" do you feel right now? (3) How "CLUMSY" do you feel right now? (4) How "ALERT" do you feel right now? (5) How "DIZZY" do you feel right now? (6) How "CONFUSED" do you feel right now? (7) How "ENERGETIC" do you feel right now? (8) Are you in a "GOOD MOOD" right now? (9) How "DAZED" do you feel right now? (10) How "EXCITED" do you feel right now? (11) How "SLEEPY" do you feel right now? (12) How "DEPRESSED" do you feel right now? (13) How "EUPHORIC" do you feel right now? (14) Are you experiencing an "IRREGULAR HEARTBEAT" right now? (15) Do you feel as if you would have "DIFFICULTY WALKING" right now? (16) How "TALKATIVE" do you feel right now? (17) Are your "MUSCLES TWITCHING" right now? (18) How "DROWSY" do you feel right now? (19) How "NAUSEOUS" do you feel right now? (20) How "DRUNK" do you feel right now? (21) How "NERVOUS" do you feel right now? (22) How "FATIGUED" do you feel right now? (23) Is your "HEART RACING" right now? (24) How "IRRITABLE" do you feel right now? (25) How "RESTLESS" do you feel right now? (26) How "LAZY" do you feel right now? (27) How "SHAKY" do you feel right now? (28) How "RELAXED" do you feel right now? (29) How "TIRED" do you feel right now? (30) How "SLUGGISH" do you feel right now? (31) How "SWEATY" are you right now? (32) How "SPACED OUT" do you feel right now?

Drug Effect-Questionnaire (DEQ)-VAS

Individual questions are presented sequentially, one at a time. Subjects rate their response to each question by marking a 100-unit line anchored with "Not at All" on the left side and "Extremely" on the right side.

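### Aim 2 infers attenuation or augmentation from either of two F tests at 5%, on peak and again on AUC, with no deciding item, summary or error control across 55 questionnaire items

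*Combined protocol and SAP*

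**What the plan says.** Section 7 (Data Analysis, Aim 2) announces: "Three sets of analyses will be conducted on the subjective effect data". These are peak effect, AUC and a time course.

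- **Peak.** A two-factor repeated-measures ANOVA (cocaine × zolmitriptan). The rule reads: "A significant augmentation or attenuation of the effects of cocaine will be inferred if the main effect of the zolmitriptan or the cocaine-zolmitriptan interaction" is significant in the ANOVA.
- **AUC.** It is "analyzed in the same fashion as peak-effect data", so the same rule applies a second time.
- **Time course.** A three-factor ANOVA followed by Tukey comparisons that use the error term of the three-way interaction. No inference rule is stated here.

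Section 7 sets significance at p ≤ 0.05, and section 17 repeats it: "The alpha level will be set at 5" per cent.

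Appendix A gives the items. The Adjective Rating Scale has 32 ("Subjects rate their response to each question on a 5-point scale"), the Drug-Effect Questionnaire has 20 and the Cocaine Craving Questionnaire has 3. It defines no total or subscale score.

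Section 1 mentions drug liking for Aim 2, but only as an example: "reduce cocaine related increases on ratings of drug liking". Section 17 ranks the outcomes as a class: "Secondary outcome measures will be abuse-related subjective and cognitive effects of cocaine". The Aim 3 outcomes in section 7 follow the same either-test rule.

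**The concern.** The plan contains an explicit decision rule, and that rule does not hold the 5% error rate it appears to have. One item on one summary already has two chances to qualify. Multiplying by items and by summaries, with nothing named in advance as decisive, lets a claim rest on whichever combination crosses 0.05.

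Aim 2 is worded as a demonstration and has its own primary hypotheses in section 1. Section 7 reserves the exploratory label for the analyses of sex, age, race and other drug use. A significant subjective result would therefore be presented as established under the plan, although the plan gives the reader no way to separate it from chance selection among many tests.

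**Working it through.** **The plan's own figure.** The plan gives no familywise error rate. Its only related figure is 80% power for *f* = 0.27 with 20 completers at alpha 0.05. With 4 zolmitriptan levels and an assumed within-subject correlation of 0.5 (sphericity also assumed), the noncentrality is 0.27² × 20 × 4 / (1 − 0.5) = 11.66. On 3 and 57 df this gives power of 0.799. The figure reproduces, and it is for one test with no allowance for multiplicity.

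**Inputs from the documents.** Items: 32 + 20 + 3 = 55. Summaries with a stated inference rule: 2 (peak, AUC). Qualifying F tests per summary: 2. Alpha: 0.05. Completers: 20. Cells: 4 × 3 within subject.

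**Step 1, count.** 55 × 2 × 2 = 220 tests, of which 110 are on peak. Expected false positives with no zolmitriptan effect: 110 × 0.05 = 5.5 on peak and 220 × 0.05 = 11 on both.

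**Step 2, one item and one summary.** 1 − 0.95² = 9.75%.

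**Step 3, independence bound.** On peak alone, 1 − 0.95¹¹⁰ = 99.6%. Items are correlated, so this is an upper value.

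**Step 4, simulation with correlated items.** Null data for 20 subjects in 12 cells, with normal errors and equal correlation between items. The F tests are on (3, 57) and (6, 114) df, and either one qualifies. The documents give no item correlation, so a range is shown.

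| Chance of at least one false claim | 0.3 | 0.5 | 0.7 | 0.9 |
|---|---|---|---|---|
| 55 items, peak | 97% | 87% | 70% | 40% |
| 55 items, peak plus AUC | 99% | 94% | 81% | 50% |

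A second simulation built peak and AUC from four assumed post-dose readings. It gave 97/93/76/44% and 99/97/85/52%.

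**Step 5, narrower readings.**

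- *One total score per questionnaire (not stated in the plan).* Peak: 3 × 2 = 6 tests, 1 − 0.95⁶ = 26%. Peak plus AUC: 12 tests, 1 − 0.95¹² = 46%. Both are independence bounds.
- *About 12 abuse-related items (an assumed selection of nine drug-effect and three craving items), peak only.* About 24–68% across correlations 0.9 to 0.3, either direction.
- *The same 12 items, requiring a decrease* (lower mean on active zolmitriptan than on placebo, averaged over the two active cocaine doses). 41/35/28/16% at correlations 0.3/0.5/0.7/0.9.
- *All 55 items on peak, requiring that decrease.* 76/63/43/23%.

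**Step 6, Aim 3.** Six outcomes are stated as such: discounting rate for money and for cocaine, 1-back and 2-back accuracy, inhibitory failures, and latency to inhibit. The either-test rule gives about 21–45% over the same range of correlations. Go reaction time would make seven, but section 7 describes it separately as a measure of response execution.

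**The case against.** The strongest reply has five parts.

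1. *The outcomes are secondary.* This stands. The primary outcomes are the break points, and neither the primary objective nor Aim 1 depends on Aim 2.
2. *The plan does not say that items are tested singly.* This also stands. It refers to subjective-effect data in general, whereas for the UKU side-effect scale it says explicitly that items are analysed. But no scoring is defined, so item-level claims are open, and even three totals leave a bound of 26–46%.
3. *Not every hit would support Aim 2.* Correct. A change in feeling clumsy or sleepy, or an increase in liking, does not show attenuation of abuse-related effects. Requiring direction and relevance brings the rate down to about 16–41%.
4. *Items are strongly correlated, and the simulations assume normal errors although 35 items (32 + 3) have five response categories.* The correlations are assumptions, and at 0.9 the 55-item figures fall to 40–50%. They remain many times 5%.
5. *Tukey's HSD protects the comparisons.* It does so only between means within one ANOVA, not across items or summaries.

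Two stronger readings are tempting. A reader might infer that all three analyses carry the inference rule. The time course has no stated rule, so the firm count stops at 220. A reader might also infer that a positive Aim 2 result would be close to uninformative. For a directional claim on relevant items the documents do not support that; the error rate is inflated but not near certainty.

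**Conclusion.** The point holds. As written, the Aim 2 rule carries a false-claim rate far above 5%: roughly 40–97% on peak and 50–99% on peak plus AUC if items are tested singly, 26–46% as an independence bound with three totals, and about 16–41% on peak for a directional claim on about 12 relevant items. Aim 3 stands at about 21–45% for six outcomes. These figures rest on assumed item correlations of 0.3–0.9, normal errors, and on item-level testing or item selections that the plan does not specify. No reading examined brings the rate near 5%.

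Because the outcomes are secondary and Aim 1 is untouched, this should be fixed before analysis but does not threaten the trial's main question.

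**What to change.** Before analysis, add one paragraph to the Data Analysis section that does the following.

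- **Name a small set of deciding outcomes per aim and one deciding summary.** For Aim 2, for example, peak drug liking from the Drug-Effect Questionnaire and a craving score whose calculation is defined. For Aim 3, the discounting rates for money and cocaine. These follow the examples in section 1, but the choice is the investigators'.
- **Settle the two F tests.** Either name one deciding F test per outcome, or enter both p-values per outcome into Holm. With two outcomes that means four p-values, the smallest compared with 0.05/4 = 0.0125. Applying Holm to outcomes while leaving either F test sufficient does not work: with each test at 0.025 in the first step, the rate is 1 − 0.975⁴ = 9.6% under independence. Done properly, this holds familywise error at 5% within each aim.
- **Require the effect to be attenuating**, and state the contrast by which direction is judged.
- **Report the rest without inferring attenuation.** The other items, AUC, the time course and the remaining tasks are exploratory or carry false-discovery-rate q-values.

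The cost is one paragraph, with no new data or subjects. The downside is that fewer items can be called significant.
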